18. CLINICAL STUDY REPORT

A clinical study report (CSR) will be written and distributed to health authorities as required by applicable regulatory requirements.

Note: EU Regulation (EC) No.1901/2006, states: For pediatric studies the CSR must be distributed to the applicable health authorities within 6 months of completion of the study.

19. PUBLICATION OF DATA AND PROTECTION OF TRADE SECRETS

Roche will comply with the requirements for publication of study results.

The results of this study may be published or presented at scientific meetings. If this is foreseen, the investigator agrees to submit all manuscripts or abstracts to Roche prior to submission. This allows the Sponsor to protect proprietary information and to provide comments based on information from other studies that may not yet be available to the investigator.

In accordance with standard editorial and ethical practice, Roche will generally support publication of multicenter trials only in their entirety and not as individual center data. In this case, a coordinating investigator will be designated by mutual agreement.

Authorship will be determined by mutual agreement and in line with International Committee of Medical Journal Editors authorship requirements. Any formal publication of the study in which contribution of Roche personnel exceeded that of conventional monitoring will be considered as a joint publication by the investigator and the appropriate Roche personnel.

Data derived from RCR or any other biomarker specimen analysis on individual subjects will not be provided to study investigators, except where explicitly stipulated in a study protocol (e.g., if the result is an enrollment criterion). Exceptions may be granted (e.g., if biomarker data would be linked to safety issues). The aggregate results of any research conducted using RCR or any other biomarker specimens will be available in accordance with the effective Roche policy on study data publication.

Any inventions and resulting patents, improvements and/or know-how originating from the use of the RCR or any other biomarker will become and remain the exclusive and unburdened property of Roche, except where agreed otherwise.

Appendix 1 Liver Biopsy Scores

Various liver biopsy classification systems may be used for entry into this study. Some examples are included below.

Scores considered as advanced fibrosis will be Metavir fibrosis 3, Knodell fibrosis score 3, Modified Ishak fibrosis score 4, Batts & Ludwig score 3, or *Scheuer score 3*. Subjects with these scores will be assigned to Group C.

Scores considered as cirrhosis will be Metavir fibrosis 4, Knodell fibrosis score 4, Modified Ishak fibrosis score 5 and 6, Batts & Ludwig score 4, or *Scheuer score 4*. Subjects with these scores are excluded from the study.

METAVIR FIBROSIS SCORE

0. no fibrosis
1. stellate enlargement of portal tract but without septa formation
2. enlargement of portal tract with rare septa formation
3. numerous septa without cirrhosis
4. cirrhosis

KNODELL FIBROSIS SCORE

0. no fibrosis
1. fibrous portal expansion
3. bridging fibrosis (portal-portal or portal-central linkage)
4. cirrhosis

MODIFIED ISHAK FIBROSIS SCORE

0. no fibrosis
1. fibrous expansion of some portal areas, with or without short fibrous septa
2. fibrous expansion of most portal areas, with or without short fibrous septa
3. fibrous expansion of most portal areas, with occasional portal to portal (P-P) bridging
4. fibrous expansion of portal areas, with marked bridging (P-P) as well as portal-central (P-C)
5. marked bridging (P-P and/or P-C) with occasional nodules (incomplete cirrhosis)
6. cirrhosis, probable or definite

Appendix 1 Liver Biopsy Scores (cont.)

BATTS & LUDWIG

0. no fibrosis; normal connective tissue
1. portal fibrosis; fibrous portal expansion
2. periportal fibrosis; periportal or rare portal-portal septa
3. septal fibrosis; fibrous septa with architectural distortion; no obvious cirrhosis
4. cirrhosis

SCHEUER FIBROSIS SCORE

0. *None*
1. *Enlarged fibrotic portal tracts*
2. *Periportal or portal -portal septa but intact architecture*
3. *Fibrosis with architecture distortion but no cirrhosis*
4. *Probable or definite cirrhosis*

Appendix 2 Child-Pugh Classification of Severity of Liver Disease

Clinical and Biochemical Measurements	Points Scored for Increasing Abnormality		
	1	2	3
Encephalopathy (grade) ^a	None	1 or 2	3 or 4
Ascites ^b	Absent	Slight	Moderate
Bilirubin (µmol/L)	<34	34-50	>50
Albumin (g/L)	>35	28-35	<28
Prothrombin time prolongation (seconds prolonged) OR	<4	4-6	>6
Prothrombin time (International Normalized Ratio)	<1.7	1.7-2.3	>2.3

^a According to grading of Trey, Burns, and Saunders (1966).

^b As determined by physical examination alone.

1, 2, or 3 points are scored for increasing abnormality of each of the 5 parameters measured.

Class A: 5 or 6

Class B: 7 to 9

Class C: 10 to 15

Appendix 3

ICH Guidelines for Clinical Safety Data Management, Definitions and Standards for Expedited Reporting, Topic E2

A serious adverse event is any experience that suggests a significant hazard, contraindication, side effect, or precaution. It is any AE that at any dose fulfills at least one of the following criteria:

- Is fatal (results in death) (Note: Death is an outcome, not an event.)
- Is life-threatening (Note: the term “life-threatening” refers to an event in which the subject was at immediate risk of death at the time of the event; it does not refer to an event which could hypothetically have caused a death had it been more severe.)
- Requires in-patient hospitalization or prolongation of existing hospitalization
- Results in persistent or significant disability/incapacity
- Is a congenital anomaly/birth defect
- Is medically significant or requires intervention to prevent one or other of the outcomes listed above.

Medical and scientific judgment should be exercised in deciding whether expedited reporting to the Sponsor is appropriate in other situations, such as important medical events that may not be immediately life-threatening or result in death or hospitalization but may jeopardize the subject or may require intervention to prevent one of the outcomes listed in the definitions above. These situations should also usually be considered serious.

Examples of such events are intensive treatment in an emergency room or at home for allergic bronchospasm; blood dyscrasias or convulsions that do not result in hospitalization; or development of drug dependency or drug abuse.

An unexpected AE is one in which the nature or severity is not consistent with the applicable product information.

Table 2	Schedule of Assessments and Procedures—Group B (Untreated Control)	36
Table 3	Schedule of Assessments and Procedures—Switch (PEG-IFN).....	40

LIST OF FIGURES

Figure 1	Schematic of Study Design	8
Figure 2	Potentially Clinically Relevant Laboratory Abnormalities for Neutrophil, Lymphocyte, Platelet Counts, Hemoglobin, Triglyceride Concentration and ALT	19

LIST OF APPENDICES

Appendix 1	Protocol Synopsis	24
Appendix 2	Schedule of Assessments	31

GLOSSARY OF ABBREVIATIONS

ACTG	AIDS Clinical Trials Group
AE	Adverse event
ALP	Alkaline Phosphatase
ALT	Alanine aminotransferase
anti-HBe	Hepatitis B envelope antibody
anti-HBs	Hepatitis B surface antibody
AST	Aspartate aminotransferase
AUC	Area under the curve
BMI	Body mass index
BSA	Body surface area
CHB	Chronic hepatitis B
CL/F	Clearance
C_{max}	Maximum concentration
CSR	Clinical Study Report
DAIDS	Division of AIDS
DAP	Data analysis plan
DBP	Diastolic blood pressure
DNA	Deoxyribonucleic acid
DSMB	Data Safety Monitoring Board
FPE	First patient enrollment
FT3	Free triiodothyronine
FT4	Free thyroxin

GGT	Gamma glutamyl transpeptidase
HBeAg	Hepatitis B envelope antigen
HBsAg	hepatitis B surface antigen
HBV	hepatitis B virus
HBV-DNA	Hepatitis B DNA
ITT	Intent-to-treat
IxRS	Interactive voice or web response system
LLN	Lower limit of normal
LOCF	Last observation carried forward
LSM	Liver Stiffness Measure
LTFU	Long term follow-up
MedDRA	Medical Dictionary for Regulatory Activities
PCR	Polymerase chain reaction
PD	Pharmacodynamic
PEG-IFN	Pegylated-interferon alfa-2a
PK	Pharmacokinetic
PT	Preferred Term
RNA	ribonucleic acid
SAE	Serious adverse event
SAP	Statistical Analysis Plan
SBP	Systolic blood pressure
SD	Standard deviation
SI units	International System of Units

SOC	System Organ Class
TBG	Thyroxine-binding globulin
TPO	Thyroid peroxidase
TSH	Thyroid-stimulating hormone
ULN	Upper limit of normal
V/F	Volume of distribution/bioavailability

1. **BACKGROUND**

This randomized, controlled, parallel-group, open-label, multicenter study in children with hepatitis B envelope antigen (HBeAg) positive chronic hepatitis B (CHB) in the immune active phase will compare efficacy and safety between a group treated with pegylated interferon alfa-2a (PEG-IFN) monotherapy and an untreated control group, and evaluate pharmacokinetics (PK) of PEG-IFN following administration of a new body surface area (BSA)-based dosing regimen.

The rationale for conducting a randomized controlled study in pediatric patients with CHB is to establish the efficacy and safety of PEG-IFN treatment in this pediatric immunoinactive population.

This statistical analysis plan (SAP, which is also known as Data Analysis Plan [DAP] Module 1) describes the data handling rules and statistical analysis methods to be used for the analysis of the clinical data from the phase IIIb study YV25718. The layout of tables, listings and figures will be provided in DAP Module 2; the data specification will be addressed in DAP Module 3.

[figure not shown]
2. **STUDY DESIGN**

This is a 2:1 randomized, controlled, parallel-group, open-label, multicenter study of PEG-IFN treatment compared to an untreated control ([Figure 1](#)). Patients without advanced fibrosis/cirrhosis will be randomized 2:1 to PEG-IFN treatment (Group A) or untreated control (Group B), respectively. Patients with advanced fibrosis will be assigned to PEG-IFN treatment (Group C). Patients in Groups A and C will receive PEG-IFN for 48 weeks. The first 48 weeks from randomization will be referred to as the treatment period for Groups A and C and the principal observation period (this is also the untreated control observation period in [Figure 1](#)) for Group B. The primary endpoint will be assessed 24 weeks after the end of treatment/principal observation period.

Forty-eight weeks after randomization, PEG-IFN will be offered to patients in the Group B untreated control group who have not experienced HBeAg seroconversion. This offer will be available for up to 1 year following Week 48. If eligible, these patients will enter the Switch arm, where they will receive PEG-IFN for 48 weeks.

The screening period will be up to 35 days. All patients will be followed up for 5 years after the end of treatment/principal observation period. For Group A, Group B non-switch, and Group C patients the study length is approximately 6 years (1-year treatment/principal observation period and 5 years of follow-up). For Group B switch patients the study length is up to approximately 8 years (1-year principal observation period, up to 1 year follow-up whilst deciding whether to switch, 1-year switch treatment period, and 5-year follow-up period).

Figure 1 Schematic of Study Design¹

¹ The untreated control observation period is the same as the principal observation period.

2.1 PROTOCOL SYNOPSIS

The Protocol Synopsis is in Appendix 1. For additional details, see the Schedule of Assessments in Appendix 2.

2.2 STUDY OUTCOME MEASURES

This study will compare efficacy and safety between a group treated with PEG-IFN monotherapy and an untreated control group, and evaluate pharmacokinetics (PK) of PEG-IFN following administration of a new BSA-based dosing regimen.

Details of the study objectives could be found in the Protocol Synopsis as in Appendix 1.

2.3 DETERMINATION OF SAMPLE SIZE

Sample size is based on the χ^2 test statistic. Assuming a 32% HBeAg seroconversion rate for Group A (PEG-IFN) and 10% for Group B (untreated control), a total sample size of 145 patients provides at least 80% power at the 0.05 level of significance with a two-sided χ^2 test². The sample size shall be increased by 10% and rounded to 160 patients to allow for advanced fibrotics (Group C).

2.4 ANALYSIS TIMING

The clinical data cut for the primary analysis is determined based on the comparison of primary efficacy endpoint between Group A and Group B, i.e. 24 weeks after the end of treatment/principal observation period.

The primary CSR will present the study results of efficacy, safety and pharmacokinetics on data up to the initial 24 weeks follow up after the end of treatment/principle observation period from Group A and B. Results from Group C from enrollment to 24 weeks after the end of treatment will be summarized separately in the primary CSR. Data from the Switch arm will not be mature for reporting and interpreting, thus only a summary of patient disposition, patient listings for deaths, SAEs and AEs leading to discontinuation of study treatment as of the cutoff date when all patients in Group A and Group B had their visits at 24 weeks after the end of treatment/principal observation period will be provided in the primary CSR.

The final analysis will be performed at the end of the extended long-term follow-up (LTFU) period of the study, i.e. 5 years after the end of treatment/principal observation period for all patients (including patients who switched to PEG-IFN treatment from Group B). Long term efficacy and safety data from Group A, B, C, along with all data from the Switch arm will be summarized in the final CSR.

² At least 130 patients must be evaluable for the primary endpoint, as required by Pediatric Investigational Plan.

3. STUDY CONDUCT

3.1 RANDOMIZATION ISSUES

After signing informed consent/assent and meeting screening parameters, patients without advanced fibrosis or cirrhosis (assessed by liver biopsy performed within 2 years prior to baseline) will be randomized 2:1 into the PEG-IFN treatment (Group A) or untreated control (Group B) respectively. Stratification will be performed by genotype (A versus non-A) and ALT (<5xULN versus ≥5xULN). Patients with advanced fibrosis (assessed by liver biopsy performed within 9 months prior to baseline) will be assigned to PEG-IFN treatment (Group C). Patients in Group A and Group C will receive PEG-IFN for 48 weeks. Group and dose, if applicable, will be assigned by an interactive voice or web response system (IxRS).

The randomization list for the study was created by the IxRS vendor using their internal validated process. The study statistician reviewed a dummy randomization list that was created using the same validated process.

3.2 DATA MONITORING

Starting from 8-10 months after first patient enrollment (FPE) and then approximately every 6 months thereafter, an external Data Safety Monitoring Board (DSMB) will review individual and aggregate safety data on a routine basis (see DSMB charter). Enrollment will be suspended and/or the study will be halted if serious concerns about safety are raised pending further analysis and review. Enrollment and/or study re-start will resume only if the DSMB and the Sponsor are satisfied with the safety of treatment.

4. STATISTICAL METHODS

All analyses for comparing the PEG-IFN treatment (Group A) with untreated control (Group B) are presented in [Section 4.3](#) to [Section 4.6](#). Analyses for Group C and the Switch arm will be presented in [Section 4.7](#) and [Section 4.8](#) respectively.

4.1 ANALYSIS POPULATIONS

All patient populations will be defined and determined prior to the database lock for the primary CSR. All analyses below are planned for the primary CSR unless otherwise specified. Analyses for data in LTFU period will be summarized in final CSR.

Analysis populations described in [Section 4.1.1](#) to [Section 4.1.3](#) are defined for Group A and Group B. Analysis of all efficacy endpoints will be based primarily on the Intent-to-treat (ITT) population. In addition Per Protocol (PP) population will be used for the primary endpoint. Safety analyses will be performed based on the Safety population.

Patients who have advanced fibrosis (diagnosed on liver biopsy) will receive PEG-IFN treatment in an advanced fibrotic arm (Group C). Efficacy analyses and safety analyses will be reported from all patients in Group C who receive at least one dose of study

medication.

The Switch arm includes patients randomized to Group B who opt to switch to initiating treatment with PEG-IFN after Week 48. Efficacy and safety data will be reported from all patients entering the switch arm if at least one dose of study medication was taken.

4.1.1 Intent-to-treat (ITT) Population

For Group A, the ITT population shall include all patients who receive at least one dose of study medication. For the untreated Group B, the ITT population shall include all randomized patients. Patients will be assigned to the group to which they were randomized.

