An untreated control arm has been selected for this study as the use of a placebo control arm is not considered appropriate for several reasons. Firstly, the use of placebo injections would not effectively blind treatment as the known adverse effects of IFN therapy, particularly influenza-like illness, would not occur. It would therefore be likely that subjects/parents would become aware that the subject was not receiving IFN resulting in a potential risk of noncompliance. Secondly, it would be unethical to administer weekly placebo injections for 48 weeks as administration requires an invasive procedure with an associated risk of injection-site infections and no associated benefit. A further benefit of using an untreated control arm is that the study burden for the untreated subjects is reduced as their visit schedule is less frequent compared with that of the treated subjects, which they would have to match in a placebo-controlled study. Importantly, an open-label study design does not introduce significant bias in the primary analyses, because the primary efficacy endpoints are objective and unaffected by presence of blinding. The risk of bias being introduced is further minimized with current procedures, including use of central randomization, use of a central laboratory and standardized assays, and the choice of the intent-to-treat (ITT) population for the primary analysis.

The objective of this study would be therefore to establish the benefit–risk balance for treatment using PEG-IFN in this immunoactive pediatric population, by comparing the safety and efficacy of 48 weeks treatment with an untreated control group.

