8.2.4 Analysis Populations

8.2.4.1 ITT Population

For Group A, the ITT population shall include all subjects who receive at least one dose of study medication. For the untreated Group B, the ITT population shall include all subjects with at least the baseline efficacy or safety data. For the ITT population,

subjects will be analyzed according to the groups to which they were randomized. Subjects in Group B who switched to receive PEG-IFN after Week 48 and prior to 24 weeks post-observation period will be counted as non-responders.

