8.2.5.1 Exclusion of Data from Analysis

8.2.5.1.1 Intent-to-Treat Population

All subjects randomized will be included in the ITT population, as defined in Section [8.2.4.1](#).

Subjects will be assigned to groups as randomized for analysis purposes.

Subjects will be excluded if they do not meet ITT criteria, as defined in Section [8.2.4.1](#).

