4.4.1 Primary Efficacy Endpoint

4.4.1.1 Definition of Primary Efficacy Endpoint

The primary efficacy endpoint is HBeAg seroconversion at 24 weeks after the end of treatment/ principal observation period for Group A and Group B. HBeAg seroconversion

is defined as absence of HBeAg (that is, a negative result for HBeAg) and presence of anti-HBe (that is, a positive result for anti-HBe).

The response rate of HBeAg seroconversion for a particular analysis population will be determined by:

$$\frac{\text{The number of patients with Negative HBeAg and Positive HBeAb at each visit}}{\text{The number of patients in each group for that analysis population}} \times 100\%.$$

Patients without either HBeAg or anti-HBe at 24 weeks after the end of treatment/principal observation period will be counted as non-responders. Patients in Group B who switched to receive PEG-IFN after Week 48 and prior to 24 weeks post-observation period will also be counted as non-responders.

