4.4.1.3 Sensitivity Analysis for Primary Endpoints

In addition to the stratified statistical tests, unstratified tests such as Pearson chi-square test and Fisher's exact test will be performed.

In the primary efficacy analysis, patients with missing values of primary endpoint will be considered as non-responders. In order to evaluate the robustness, sensitivity analysis will be carried out using CMH test, where missing values will be imputed with the approach of last observation carried forward (LOCF).

³ which is a superiority test.

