For consenting/assenting subjects in the site specific PK sub-study, additional visits will also be required for PK blood sampling. When adequate PK data have been collected over the first 24 weeks for at least 15 PEG-IFN-treated subjects, ideally with representation from all BSA categories, exposure will be analyzed and if necessary an adjustment will be made to the dosing regimen. Once PK data up to Week 24/switch Week 24 are available for at least 5 to 10 subjects in each BSA category, subject PK sampling will be stopped. However, the sub-study may be stopped even if data from a minimum of 5 subjects in each BSA category are not obtained in the case of excessively long recruitment times.

Those subjects that do not complete the treatment period should still return for all follow-up visits. As well as evaluation during the initial 24 weeks post-end of treatment/principal observation period, all subjects will be followed up annually for 5 years after the end of treatment/principal observation period. Safety assessments at these extended long-term follow-up visits will include evaluation of persisting AEs which were initially reported prior to follow-up Week 24, assessment of new-onset SAEs (including neuro-psychiatric events) and non-serious AEs of special interest related to PEG-IFN, deaths, thyroid function, and growth (weight and height).

Standard measures will be taken in this study to minimize the pediatric subjects' possible pain and distress.

STATISTICAL ANALYSES

Sample Size

Sample size is based on the χ^2 test statistic. Assuming a 32% HBeAg seroconversion rate for Group A (PEG-IFN) and 10% for Group B (untreated control), a total sample size of 145 subjects provides at least 80% power at the 0.05 level of significance with a two-sided χ^2 test. The sample size shall be increased by 10% and rounded to 160 subjects to allow for advanced fibrotics (Group C) and withdrawals.

Populations

ITT population: For Group A, the ITT population shall include all subjects who receive at least one dose of study drug. For the untreated Group B the ITT population shall include all subjects with at least the baseline efficacy or safety data. For the ITT population subjects will be analyzed according to the groups to which they were randomized.

Subjects in Group B who switched to receive PEG-IFN after Week 48 and prior to 24 weeks post-observation period will be counted as non-responders.

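### The primary ITT set requires a dose in Group A but only randomization in Group B, and no planned efficacy analysis includes all randomized children

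*SAP*

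**What the plan says.** SAP 4.1.1 has one entry rule per arm. For PEG-IFN: "For Group A, the ITT population shall include all patients who receive at least one dose of study medication". For control: "For the untreated Group B, the ITT population shall include all randomized patients". Its last sentence assigns children to the group to which they were randomized. That settles the arm label but not who is in the set.

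SAP 4.4.1.1 divides the responders by "The number of patients in each group for that analysis population". SAP 4.4.1.3 adds that "patients with missing values of primary endpoint will be considered as non-responders". Protocol 8.2.3 and SAP 4.4 base the primary superiority test on this ITT set.

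The protocol words the control-arm rule differently. In section 8.2.4.1, for Group B, "the ITT population shall include all subjects with at least the baseline efficacy or safety data". The protocol synopsis says the same, as does the synopsis reproduced in SAP Appendix 1: "For the untreated Group B the ITT population shall include all subjects with at least the baseline efficacy or safety data". Protocol 8.2.5.1.1 states "All subjects randomized will be included in the ITT population, as defined in Section" 8.2.4.1, then excludes anyone who does not meet that section's criteria.

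Protocol 3.1.1.1 lists "the choice of the intent-to-treat (ITT) population for the primary analysis" among the procedures that limit bias in this open-label trial.

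**The concern.** An intention-to-treat comparison keeps the groups that randomization formed. Here a Group A child must also do something after allocation is known, namely receive a dose, before being counted. A family that changes its mind on learning the allocation is treated differently by arm: in Group A the child leaves the denominator, and in Group B the child remains and counts as a non-responder if no result is obtained.

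Undosed children would be expected to seroconvert less often than dosed ones, so removing them tends to raise the Group A rate. The direction reverses only if undosed children respond more often than dosed children, that is, above 32% under the planning assumption.

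At stake is the primary test, and the protection that the protocol claims from ITT in a trial without blinding.

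**Working it through.** **1. Does any planned analysis restore the full randomized set?**

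| Analysis | Group A | Group B |
|---|---|---|
| ITT, SAP 4.1.1 | at least one dose | randomized |
| Per protocol, SAP 4.1.2 | at least one dose, no listed violation | randomized, no listed violation |
| Safety, SAP 4.1.3 | dose and a post-baseline safety assessment | post-baseline safety assessment |
| Pearson and Fisher tests, SAP 4.4.1.3 | same set, different test | same |
| LOCF, SAP 4.4.1.3 | same set, different imputation | same |

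Secondary and subgroup analyses also use ITT. SAP 4.2 summarizes withdrawals among randomized children and lists exclusions, so a reader could count them, but that is disposition and not a treatment comparison. No efficacy analysis uses all randomized children.

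**2. The plan's own sample size.** Inputs (SAP 2.3 and 3.1, protocol 8.2.2): 32% against 10%, 2:1, two-sided 0.05, total 145 for at least 80% power. The two-proportion formula gives 42 + 84 = 126 without continuity correction and 48 + 96 = 144 with it, so 145 is reproduced to within one subject. The sample size is not in question.

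At 97:48, by the pooled-variance normal approximation without continuity correction:

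- pooled rate = (97 × 0.32 + 48 × 0.10)/145 = 0.2472
- null SE = √[0.2472 × 0.7528 × (1/97 + 1/48)] = 0.0761
- alternative SE = √[0.32 × 0.68/97 + 0.10 × 0.90/48] = 0.0642
- power = Φ[(0.22 − 1.96 × 0.0761)/0.0642] = 86.5%

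**3. Effect of undosed children.** Let k of the 97 Group A children be undosed and respond at rate r, with 32% among the dosed. Both k and r are assumptions.

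- All-randomized rate p = [0.32 × (97 − k) + r × k]/97
- Odds ratio = [p/(1 − p)]/[0.10/0.90]; at p = 0.32 this is 4.24

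Example, k = 5 and r = 0: p = 0.32 × 92/97 = 29.44/97 = 30.4%, odds ratio 3.92.

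| k | r = 0 (upper bound): rate, OR, power | r = 10%: rate, OR, power | Power, planned set at same k |
|---|---|---|---|
| 0 | 32.0%, 4.24, 86.5% | 32.0%, 4.24, 86.5% | 86.5% |
| 2 | 31.3%, 4.11, 84.6% | 31.5%, 4.15, 85.2% | 86.3% |
| 5 | 30.4%, 3.92, 81.3% | 30.9%, 4.02, 83.0% | 85.9% |
| 8 | 29.4%, 3.74, 77.6% | 30.2%, 3.89, 80.7% | 85.5% |

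With r = 32% nothing changes.

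**4. Effect on false positives.** Suppose the true all-randomized rate is 10% in both arms and undosed children never respond. The chance of wrongly favouring PEG-IFN rises from 2.5% to about 2.8% with 3 undosed, 3.0% with 5 and 3.8% with 10.

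**5. Illustration near the threshold (Pearson test).** All randomized, 23/97 against 5/48: p = 0.056. With three undosed non-responders removed, 23/94 against 5/48: p = 0.047.

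**The case against.** The strongest reply is that few children, perhaps none, would be affected. Protocol 5.3 says the first dose should be given at the baseline visit, and eligibility is settled before randomization. No passage supports 5 or 8 undosed children. This stands: those counts are assumptions, and with 2 undosed the Group A rate moves by less than one percentage point.

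Second, the protocol and both synopses do set an entry condition for Group B (baseline data), so the imbalance is narrower there than in SAP 4.1.1. That is true, but the conditions are not equivalent. Baseline data can exist before allocation is known, whereas the dose comes after it.

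Third, protocol 3.1.1.1 rests first on an objective endpoint and names ITT as only one of several safeguards. That is also true. However, an objective endpoint protects the measurement, not membership of the analysis set.

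Fourth, with k children undosed the planned set loses power too, so the like-for-like cost of changing the set at k = 5 is 85.9% to 81.3% in the upper bound, not 86.5% to 81.3%. This is correct, and the last column of the table shows the right comparator.

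Fifth, Group A follow-up visits are timed from the end of treatment or from treatment withdrawal, so the schedule has no track for a child who never started. A child who stops after one dose may also reach follow-up Week 24 much earlier than Week 72. Both points stand. The first has to be handled in the fix; the second is a timing question for early stoppers that already exists in the plan.

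**Conclusion.** The concern holds. The set called ITT excludes Group A children on a post-allocation event and applies no such exclusion to Group B, and no planned efficacy analysis corrects this. The likely direction favours PEG-IFN, provided undosed children respond less often than dosed ones.

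The size depends on an unknown count. With none undosed it is nil. With 2 to 8 of 97 undosed, the Group A rate is overstated by 0.7 to 2.6 percentage points if they never respond (32.0% against 31.3% to 29.4%), and by 0.5 to 1.8 points if they respond at the control rate (32.0% against 31.5% to 30.2%). These figures assume 97:48 and 32% among dosed children.

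The effect is small and would matter mainly for a result near the significance threshold. The rule should nevertheless be changed, because it falls on the primary test of an open-label trial and the documents disagree about it. The Group B rule differs between SAP 4.1.1 and the other three places, although few children would be affected, and protocol 8.2.5.1.1 claims to include all randomized subjects under a definition that omits some of them.

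**What to change.** Use one definition in SAP 4.1.1, protocol 8.2.4.1 and both synopses, for example:

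> *ITT comprises every child randomized to Group A or Group B, dosed or not, analysed in the randomized group. The observed HBeAg and anti-HBe result 24 weeks after the treatment or principal observation period is used. If it is missing, the child is a non-responder, in either group.*

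- Leave the existing rule for Group B children who switch unchanged.
- State that, for a Group A child never dosed, the endpoint visit is Week 72 from randomization: 48 + 24 weeks, since protocol 3.1 counts the 48-week period from randomization.
- Delete the exclusion sentence in protocol 8.2.5.1.1.
- Keep the dosed set for safety and per-protocol analyses, or as a sensitivity analysis under another name.

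The cost is a few sentences, settled before the database lock at which SAP 4.1 fixes the populations. No new type of assessment is needed. A Week 72 visit would have to be scheduled for any never-dosed child; the protocol synopsis already asks children who do not complete treatment to return for all follow-up visits, and a missed visit falls under the non-responder rule. The reported Group A rate may be slightly lower, with power as tabulated. If every child is dosed, nothing changes for Group A.
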